3 GENERAL ANALYSIS AND REPORTING CONVENTIONS

This section discusses general policies to be employed in the analysis and reporting of the data from the study. Departures from these general policies may be provided in the specific detailed sections of this SAP. When this situation occurs, the rules set forth in the specific section take precedence over the general policies.

Each active dose will be presented separately in summaries and analyses as appropriate.

All continuous study assessments will be summarized by treatment and time point (as applicable) using the descriptive statistics n, mean, SD, median, and range (minimum, and maximum). All of the categorical study assessments will be summarized by treatment and time point (as applicable) using frequency counts and rates of occurrence (%). Changes from baseline for continuous outcomes will be presented as their corresponding continuous measures for post-baseline visits. All study data will be listed by dose, subject, and time point (as applicable).

No preliminary rounding will be performed; rounding will only occur after the analysis. To round, consider the digit to the right of the last significant digit: if <5, then round down; if ≥5, then round

up. Means and medians will be presented with one more decimal place than the precision of the data. Standard deviations will be presented with two more decimal places than the precision of the data. Percentages will be presented with one decimal place. A percentage of 100% will be reported as 100%. Minimums and maximums will be presented with the same precision as the original data.

All analyses will be performed using the SAS System® version 9.3 or higher. The domain (Study data tabulation Model [SDTM]) and analysis (Analysis Data Model [ADaM]) data sets will be taken as input to the SAS programs that generate the report-ready tables, figures and listings. The submission ready SDTM and ADaM data sets will be provided to the sponsor along with display deliveries.

The following conventions will be used throughout the study analysis:

- Time 0 (T0) is the time of completion of study drug administration.
- Day of surgery is defined as Day 0 (D0).
- Assessment visit times are defined by D0 and/or T0.
- Baseline value is defined as the last valid measurement prior to the dosing of study treatment.
- Change from baseline is defined as post-baseline value minus baseline value.

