8.2 Adverse Events

Any untoward medical event that occurs after signing the informed consent form (ICF) is considered to be an adverse event (AE). All AEs will be recorded through 29 days (or 36 days as applicable) or ET, after the completion of surgery. SAEs will be recorded until 30 days after the 29 day follow up visit or ET, whichever occurs earlier. Treatment-emergent AEs are defined as AEs that start or worsen in severity after the end of study treatment infiltration (post T0). Verbatim terms used by investigators to identify AEs in the CRFs will be mapped to the appropriate preferred term (PT) and system organ class (SOC) using a standardized coding dictionary (MedDRA Version 21.0). All coding will be reviewed prior to database lock. All recorded AEs will be listed, but only TEAEs will be summarized.

For evaluation of causal relatedness to treatment, the categories are probably related, possibly related or unlikely related. For categorization in the summary tables, AEs designated as probably or possibly related will be considered to be related.

For the evaluation of event severity terms, the criteria are mild, moderate, severe or potentially life-threatening.

In addition to a listing of all TEAEs, treatment related TEAEs, serious TEAEs, Deaths, and TEAEs leading to premature discontinuation from the study will be provided.

An overall summary will be prepared giving for each treatment group and overall both the number of TEAEs, and the number of subjects with at least one TEAEs, as well as SAEs, treatment related TEAEs and TEAEs leading to premature discontinuation from study.

The number of subjects with AEs will be summarized for each treatment group by SOC and PT sorted in alphabetically by SOC, and then by PT within SOC. These summaries will be given by treatment in separate tables for each of the following TEAE event sets:

- All events
- Treatment related events
- Serious events
- Events leading to premature discontinuation from study
- Events by maximum severity

If a given subject experiences a TEAE that maps to the same PT/SOC more than once, the subject will be counted only once for the SOC/PT at the greatest severity (i.e., mild, moderate, or severe) and causality (i.e., attribution to study material).

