Duration of a TEAE lasting more than 24 hours will be computed in days as the stop date of the event minus the start date plus 1 and will be reported in days. TEAEs lasting less than 24 hours will be computed as stop date/time minus start date/time. If reported as ongoing at the time of database lock, the stop date is defined as the date of the last visit or the last date of any event for the subject in the database, whichever is later. If a TEAE is considered resolved, but the stop date is missing, the last day of the month will be imputed if the month and year are available. If only the year is available, and the year is the same as the year of the last visit, the stop date will be the latest of the last visit date or latest event for the subject in the database. If the year of the event is prior to the year of the last treatment, the end day and month will be set to 31 December.

For missing or partial start and stop dates/times, the most conservative imputation will be used (AEs will be assumed to be temporally related to the study medication). [Table 8-1](#) will be used to impute any missing dates/times:

Table 8-1 Table of Imputation Rules for Missing AE Start Dates

Missing Date Portion	Prior to Treatment	Same as Treatment Start Date	After Treatment Start Date
Day	Month and Year < Month and Year of Study treatment:	Month and Year = Month and Year of Study treatment:	Month and Year > Month and Year of Study Treatment:
	Start Day = 1 Stop Day=last day of the month	Start Day = Day of first treatment Stop Day= last day of the month	Start Day = 1 Stop Day=last day of the month
Day and Month Define Day as above, then:	Year < Year of first treatment:	Year = Year of study treatment:	Year > Year of study treatment:
	Start Month = July Stop Month = Dec	Start Month = Month of study treatment Stop Month = Dec	Start Month = January Stop Month = Dec
Day, Month, and Year	To be conservative, completely missing start dates will be imputed using the date of study treatment, Missing end dates will be imputed using date of last study contact with the subject		
Time	Missing start times will be imputed as 00:01 Missing stop times will be imputed as 23:59		

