After following these imputation rules, if the start date/time is imputed as a date after the end date/time, the start date/time will be set to the end date/time to provide a positive duration for the event incidence.

Missing assessments for AE study medication relationship or severity will be analyzed as related or severe respectively. No other imputation is planned for safety data.

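### SAP Table 8-1 sets a missing AE start time to 00:01 even on the treatment day, so, read literally, an untimed Day-0 AE is not treatment-emergent

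*SAP*

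**What the plan says.** SAP 8.2 makes treatment emergence depend on clock time: "Treatment-emergent AEs are defined as AEs that start or worsen in severity after the end of study treatment infiltration (post T0". SAP 3 fixes the reference point: "Time 0 (T0) is the time of completion of study drug administration". SAP 8.2 also gives the consequence of failing the definition: "All recorded AEs will be listed, but only TEAEs will be summarized".

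For missing or partial dates and times, the sentence before Table 8-1 sets the principle: "the most conservative imputation will be used (AEs will be assumed to be temporally related to the study medication". The date rows follow it. A missing start day in the treatment month becomes the treatment day, a missing day and month in the treatment year become the treatment day and month, and "completely missing start dates will be imputed using the date of study treatment".

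The Time row is different. It is not divided into before, same as and after treatment. It reads "Missing start times will be imputed as 00:01", and missing stop times become 23:59.

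The Protocol defines a TEAE in more than one way. The synopsis uses onset after T0, as the SAP does. Section 15.7.1 uses onset on the date of treatment. Section 9.1.4 counts AEs from the time study treatment is administered.

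**The concern.** On Day 0 the clock time decides whether an AE is treatment-emergent, and on that day the Time row picks the earliest possible time. The rule therefore works against the principle that introduces it. It also cancels the conservative date rows: a fully missing start date is moved to the treatment day so that the AE counts, and the 00:01 start then removes it.

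Safety and tolerability is the first secondary objective. Read literally, the rule would drop these AEs from SAP Tables 14.3.1.1 to 14.3.1.3 and 14.3.1.5 to 14.3.1.7. The effect on Table 14.3.1.4 is unclear, because its title refers to SAEs while SAP 8.2 lists serious events among the TEAE sets.

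Day 0 matters for this drug. Protocol 7.1.4 says that activating the receptor causes brief hyperalgesia, redness and burning at once, although the Mayo block may mask some of this.

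**Working it through.** **Step 1: apply the current rule.** The documents give no clock time for T0, so it is varied here as an assumption. An AE dated Day 0 with no time becomes Day 0, 00:01. It is a TEAE by onset only if 00:01 is later than T0.

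| Assumed T0 | 00:01 precedes T0 by | TEAE by onset, SAP 8.2 | TEAE, Protocol 15.7.1 (date rule) |
|---|---|---|---|
| 07:00 | 6 h 59 min | No | Yes |
| 10:00 | 9 h 59 min | No | Yes |
| 14:00 | 13 h 59 min | No | Yes |
| 17:00 | 16 h 59 min | No | Yes |

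The result is the same for any T0 later than 00:01. It also holds for an untimed AE moved to Day 0 by any of the three date rules. An untimed AE dated Day 1 is a TEAE, and one dated Day -1 is not.

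**Step 2: look for a rule that rescues the event.** The paragraph after the table covers only a start imputed later than the stop, where "the start date/time will be set to the end date/time to provide a positive duration". That cannot move 00:01 to a later time. SAP 8.2 then gives rules for missing relationship and severity and plans no other imputation of safety data. The one route back is a recorded worsening after T0.

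**Step 3: size per lost event.** The planned arm size is 36, and three active arms make 3 × 36 = 108. If the lost event is a subject's only TEAE, incidence falls by:
- 1/36 = 2.8 percentage points in that arm;
- 1/108 = 0.9 points in the pooled active group.

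**Step 4: how often one event carries a subject's count.** Phase 1 (Protocol Table 2) gives subjects with TEAEs (s) and TEAEs (e). Every subject with more than one TEAE has at least two, so the number with exactly one is at least 2s − e.

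| Phase 1 group | s | e | At least 2s − e |
|---|---|---|---|
| 0.5 mg | 4 | 8 | 0 |
| 1.0 mg | 3 | 4 | 2 |
| 2.0 mg | 2 | 2 | 2 |
| 3.0 mg | 3 | 3 | 3 |
| 4.2 mg | 4 | 5 | 3 |
| Active total | 16 | 22 | 10 |
| Placebo | 4 | 6 | 2 |

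At least 10 + 2 = 12 of 16 + 4 = 20 subjects (60%) had exactly one TEAE. This says nothing about how many AEs are untimed. It shows only that losing one event can often remove a subject from the incidence count.

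**Step 5: test the proposed rule** (T0 + 1 minute on the treatment day, unless the record shows onset at or before T0), at the same four T0 values.

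| Untimed start, dated or imputed to Day 0 | TEAE |
|---|---|
| Stop recorded on Day 1 | Yes |
| Stop on Day 0, time missing (23:59) | Yes |
| Stop at T0 + 1 min | Yes |
| Stop exactly at T0 | No |
| Stop 10 min before T0 (taken as during staged administration) | No |
| Stop 60 min before T0 | No |
| Start day missing, stop recorded on Day -2 | No |

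Setting the start exactly to T0 would not work, because the definition requires onset after T0.

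**The case against.** The strongest reply is that the text has a workable reading. The introductory sentence settles timing in favour of a link to study medication, and the 00:01 and 23:59 values may serve only to compute duration. Section 8.2 does use clock times for that purpose: "TEAEs lasting less than 24 hours will be computed as stop date/time minus start date/time". This reading is sensible, but the SAP does not state it. It says that Table 8-1 is used for any missing date or time, so two programmers could produce different TEAE tables from the same data.

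A second reply is that collection already sorts Day-0 events. SAP 5.2 sends events before the study procedure to medical history, and Protocol 13.1.2 records pre-dose procedure-related AEs as non-treatment emergent. An untimed Day-0 entry on the AE form is therefore usually post-treatment. That stands, but this sorting is not part of the SAP 8.2 definition, so the derivation would still drop the event.

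A third reply is that the reach is probably very small. Subjects are observed as inpatients on Day 0, and missing onset data should be rare. This stands too. Protocol 13.1.2 lists an onset date but no onset time, while the SAP's hour-based durations imply that times are collected. The CRF is not shown.

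Finally, Protocol 15.7.1 is an imperfect benchmark, because its date rule would also count pre-dose Day-0 AEs. Protocol 15.1 leaves variable derivation and missing-data handling to the SAP, which suggests that the SAP definition governs. Neither document says so for TEAEs.

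**Conclusion.** The concern holds as a conflict within SAP 8.2. Read literally, the Time row classifies every untimed Day-0 AE without recorded later worsening as not treatment-emergent, against the principle stated just before the table. The conclusion needs only that T0 falls after 00:01 on the day of surgery. AEs with a recorded start time are unaffected.

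The severity is minor. The number of affected AEs is unknown, all AEs remain in the listings, and Protocol 15.7 plans no formal safety comparisons. Confidence is high about the text; no claim is made about how far the tables would change.

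A related point also holds and does not depend on missing times. For an AE that starts during the staged administration, SAP 8.2 and the Protocol synopsis exclude it. Protocol 15.7.1 includes it, and so does 9.1.4 if its wording is taken to mean the start of administration.

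**What to change.** Add to the Time row of Table 8-1:

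*If the start date is, or is imputed to, the day of study treatment and the start time is missing, the start time is set to T0 + 1 minute, unless the record (including a recorded stop date/time at or before T0) shows onset at or before T0. In that case, and for all other dates, 00:01 is used.*

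Treatment emergence then follows from the existing definition and the existing start-after-stop rule. The SAP should name the fields that count as the record, such as the AE dates and times and the non-treatment-emergent designation.

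Separately, add one sentence to the SAP naming the governing TEAE definition. Align the Protocol texts at the next amendment, or note the difference in the CSR.

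The cost is one sentence and one derivation line for Table 8-1, plus the sentence on the definition, before database lock and unblinding. There are two downsides. An occasional pre-T0 AE with neither start nor stop time may be counted as a TEAE. The hour-based duration of an affected AE also shortens by the clock time of T0: (T0 + 1 min) − 00:01, which is 7 h for T0 at 07:00 and 17 h for T0 at 17:00. A date-level rule that counts an untimed Day-0 AE as a TEAE unless it is documented as pre-T0, and keeps 00:01 for duration, would avoid the second downside. It would leave TEAEs in the data with an imputed start before T0.

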8.3 Surgical Site Assessment/ Wound Evaluation

Surgical site is defined as the area extending approximately 2-3 cm in all directions (lateral/medial/proximal/distal) from the incision site and surrounding tissues which may be affected by the infiltration of the Investigational Product.

At T96h prior to discharge, the investigator will evaluate their satisfaction with the healing of the wound during this Surgical Site assessment using an 11-point scale (0-10) where a score of 0 is "Completely unsatisfied," and a score of 10 is "Completely satisfied.". Surgical site wound status will be evaluated prior to discharge from the inpatient unit (T96h) and on Days 8, 15, and 29 or if necessary Day 36. Surgical site wound status will be assessed for erythema, drainage, edema, induration, and hematoma using a 5-point scale (0-4) where 0 means none and 4 means severe.

The surgical site and surgical wound assessment results will be listed and will be summarized by treatment and visit.

8.4 Physical Examination

A complete medical history and physical examination including all major body systems will be performed at Screening. In addition, an interim medical history and targeted physical examination will be performed prior to surgery (if not done on D-1), and to capture changes after surgery, at 96 hours (within 4 hours of discharge), and Days 8, 15 and 29/ET after the administration of study medication.

Physical examination results will be listed for individual subjects.

8.5 Vital Signs

Vital signs results including blood pressure (systolic and diastolic; mmHg), pulse rate (beats per minute), respiration rate (breaths/min), and body temperature will be listed for individual subjects.

Baseline for vital signs measurements will be defined as the last evaluation before dosing with study medication. Summary statistics, including change from baseline, will be determined for each measure and will be summarized by treatment and time point.

8.6 Neurosensory Assessment

Neurosensory testing at site of incision and the skin surrounding the incision will be performed at T96h (within 4 hours of discharge) and then as an outpatient on Days 8, 15, and D29/ET or if necessary Day 36.

The neurosensory assessment results will be listed and the number of subjects with normal/abnormal assessments will be summarized descriptively by treatment, target foot and time point.

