Safety Endpoints:	
The following safety endpoints will be evaluated:
 
 
• Incidence of TEAEs or treatment-emergent SAEs from D0/T0 through D29: Note that all AEs will be recorded from the time the informed consent form (ICF) is signed through D29 (or D36 as applicable). TEAEs are defined as AEs occurring post T0 (end of study treatment infiltration).
 
• Surgical site assessment / wound evaluations to assess for atypical skin reactions, e.g., erythema, pain, pruritus, bruising, swelling, bruising or other skin changes, should be evaluated and graded for severity and followed regularly until resolution or a stable baseline is achieved.
 
• Physical examination (PE) of the lower extremities and vital signs, including neurosensory testing of both lower extremities 
 
○ Note that any observed or reported sensory deficit or clinically significant persistent sensory change remote from the immediate surgical site, such as allodynia or hyperalgesia, must be designated as a neurologic AE. Subjects should be followed until resolution or a stable baseline is achieved.
 
○ Numbness proximal to the incision need not be considered a neurologic AE since this could occur because of tissue trauma and inflammation from the surgery.
 
 
 
• ECG changes from screening to T24h post-treatment
 
• Clinically significant clinical labs changes from screening
 

Pharmacokinetics:	
Approximately 1/3rd of enrolled subjects at each site will participate in the PK study (48 in total; 12 in each treatment group). The PK population will include all subjects who have sufficient concentration-time profiles for estimation of PK parameters.
 
Based upon the PK results from the Phase 1 bunionectomy ascending dose safety study, the time points for whole blood collection will be at baseline (within the 30 min before the start of study treatment dosing), and T5min, T10 min, T15min,

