#### **12.5.8. Neurosensory Exam**

A neurosensory exam of the lower extremity (foot/great toe surgical site with contralateral comparison) will be conducted at screening, at T96h prior to discharge from the inpatient unit, on the D8, D15 and D29/ET (and D36 if necessary) visits. The exam will involve the dorsal aspect of the foot proximal to the great toe.

This evaluation will include the following (details described in [Appendix 1G](#)):

- Visual exam of the foot
- Deep Tendon Reflexes (normal, reduced or absent)
- Vibratory sensation (normal, reduced or absent)

- Monofilament Sensation (normal, reduced or absent)
- Allodynia to brush (pain (allodynia), hyperesthesia, normal, reduced or absent)

A persistent atypical sensory change after EOS, such as allodynia or hyperalgesia proximal to the surgical site will be reported as an AE. Numbness at or near the incision need not be considered an AE since this could occur due to tissue trauma and inflammation from surgery.

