Table 14.3.1.5	Safety Population	Summary of TEAEs Leading to Discontinuation from Study
Table 14.3.1.6	Safety Population	Summary of TEAEs by System Organ Class, Preferred Term and Severity
Table 14.3.1.7	Safety Population	Summary of TEAEs by System Organ Class, Preferred Term and Relationship to Study Drug
Table 14.3.2.1.1	Safety Population	Summary of Blood Chemistry Laboratory Tests: Results and Change from Baseline
Table 14.3.2.1.2	Safety Population	Summary of Blood Chemistry Laboratory Tests: Shifts from Baseline
Table 14.3.2.2.1	Safety Population	Summary of Hematology Laboratory Tests: Results and Change from Baseline
Table 14.3.2.2.2	Safety Population	Summary of Hematology Laboratory Tests: Shifts from Baseline
Table 14.3.2.3.1	Safety Population	Summary of Urinalysis Laboratory Tests: Results and Change from Baseline
Table 14.3.2.3.2	Safety Population	Summary of Urinalysis Laboratory Tests: Shifts from Baseline
Table 14.3.4	Safety Population	Summary of Vital Signs: Results and Change from Baseline
Table 14.3.5	Safety Population	Summary of Surgical Site Assessment
Table 14.3.6.1	Safety Population	Summary of Neurosensory Exam –Target Foot
Table 14.3.6.2	Safety Population	Summary of Neurosensory Exam –Non-Target Foot
Table 14.3.7	Safety Population	Summary of ECG Exam Abnormal Findings

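### SAP 8.6 reduces the neurosensory exam to normal/abnormal, so no by-arm exam table shows hypersensitivity apart from expected numbness, and no shift from screening is planned

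*SAP*

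**What the plan says.** Protocol 12.6.2 names the neurosensory exam among the safety endpoints. Protocol 12.5.8 and Appendix G record it item by item for each foot. Reflexes, vibration and monofilament each have three levels (normal, reduced, absent). The brush item has five: "Allodynia to brush (pain (allodynia), hyperesthesia, normal, reduced or absent". The exam is done at screening, at T96h and at the follow-up visits.

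SAP 8.6 gives two outputs. First, "The neurosensory assessment results will be listed". Second, "the number of subjects with normal/abnormal assessments will be summarized descriptively by treatment, target foot and time point". The planned tables are 14.3.6.1, "Summary of Neurosensory Exam –Target Foot", and 14.3.6.2 for the other foot. Their titles name no items or categories.

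On where to test, Protocol 12.5.8 says "The exam will involve the dorsal aspect of the foot proximal to the great toe", while SAP 8.6 says "Neurosensory testing at site of incision and the skin surrounding the incision will be performed at T96h". On adverse events, Protocol 12.5.8 says that a persistent atypical change "such as allodynia or hyperalgesia proximal to the surgical site will be reported as an AE". The synopsis (Safety Endpoints) says that "clinically significant persistent sensory change remote from the immediate surgical site, such as allodynia or hyperalgesia, must be designated as a neurologic AE".

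**The concern.** Protocol 7.1 and 7.1.4 describe capsaicin as first exciting nociceptors, with transient hyperalgesia, and then desensitizing them. Gain and loss of sensation are therefore both relevant to this drug, and they mean different things. Near the incision the protocol expects numbness from the surgery itself and does not require it to be reported as an adverse event. It makes no such exception for allodynia.

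A normal/abnormal count cannot show which of the two occurred. Protocol 15.7 rules out formal safety comparisons, so Tables 14.3.6.1 and 14.3.6.2 are the only planned by-arm display of this exam. If they hide direction, a reader of the study report must rebuild it from the listing.

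**Working it through.** The plan states no figure for this endpoint. The only design number used below is 36 per arm, and it reproduces: 2 × (1.960 + 1.282)² × 130² / 100² = 2 × 10.51 × 1.69 = 35.5, rounded up to 36.

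**1. What the two-way summary discards, item by item (Appendix G)**
- Visual exam: recorded as normal/abnormal, so nothing is lost.
- Reflexes, vibration, monofilament: three levels become two. Grade is lost, but direction is not, because these items record only loss.
- Brush: five levels become two. Pain and hyperesthesia (gain) join reduced and absent (loss).

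SAP 8.6 does not say whether the count is per item or one overall flag. The brush problem arises either way. An overall flag would also merge visual, reflex and vibration findings.

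SAP section 3 would by default give frequency counts for categorical assessments, but it lets a specific section override the general rule. Section 8.6 is such a section.

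**2. Illustration (counts assumed, not from the documents; 36 per arm)**
- Placebo: 14 with loss only, 1 with allodynia. Abnormal = 15/36 = 41.7%.
- Active: 7 with loss only, 8 with allodynia. Abnormal = 15/36 = 41.7%.
- By direction, allodynia is 1/36 = 2.8% against 8/36 = 22.2%.

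Range: let placebo loss run from 10 to 22 and let 3, 5 or 7 subjects move from loss to allodynia on active. The pooled rate stays equal in both arms, from 11/36 = 30.6% to 23/36 = 63.9%. Allodynia is 2.8% on placebo against 4/36 = 11.1%, 6/36 = 16.7% or 8/36 = 22.2% on active.

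The equality is built in, but the loss of direction does not depend on it. Suppose active has 14 with loss and 8 with allodynia. The table then prints 22/36 = 61.1% against 41.7%. It prints the same 61.1% if active has 14 + 7 = 21 with loss and 1 with allodynia.

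**3. Screening**
Protocol Table 1, 9.1.1 and 12.5.8 require a screening exam. SAP 8.5 gives vital signs a change from baseline, and SAP 8.8 gives laboratory tests a change and a shift from screening. SAP 8.6 plans neither and does not list screening among the exam times. A deficit present before surgery would count as abnormal afterwards.

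**4. Test location, side by side**
- Synopsis, Monitored Parameters: leg and foot proximal to the incision, with the other side as control.
- Synopsis, Safety Parameter Assessment Times, and SAP 8.6: on and around the incision.
- Protocol 12.5.8: dorsum of the foot, proximal to the great toe.

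These are not the same area, and the expected amount of surgical numbness may differ between them.

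**5. Adverse-event wording, side by side**
- Synopsis, Safety Parameter Assessment Times: sensory deficits or persistent change *beyond* the area proximal to the incision must be a neurologic adverse event. Numbness at or close to the incision is exempt.
- Synopsis, Safety Endpoints: a deficit or persistent change *remote* from the site must be one. Numbness *proximal* to the incision is exempt.
- Protocol 12.5.8: allodynia or hyperalgesia *proximal* to the site is one. Numbness at or close to the incision is exempt.

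*Proximal* is not defined and could mean near or anatomically proximal. Neither synopsis rule is stated as exclusive, so the three can be read together: 12.5.8 covers the proximal area and the synopsis covers what lies further out. The wording is still uneven, because the synopsis alone gives no instruction for allodynia in the proximal area.

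**The case against.** The best defence is that the safety output does not rest on this table. Neurosensory testing is part of the interim physical examination (Protocol 12.5.6), and Protocol 15.7.4 has abnormal or clinically significant examination findings recorded as adverse events. SAP 8.2 tabulates those by preferred term, severity and relationship for each arm (Tables 14.3.1.2, 14.3.1.6 and 14.3.1.7). Every exam result is in Listing 16.2.25. No data are lost and no error rate is touched. This stands as a partial backstop. It does not cover findings that are not reported as adverse events, and a listing is not a by-arm comparison.

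Three stronger readings are tempting but not supported.
- A reader might infer that the synopsis and 12.5.8 contradict each other, so that event counts turn on which one a site follows. Neither synopsis rule says *only*, and no passage exempts allodynia near the site.
- A reader might infer that loss and gain always fall under different adverse-event rules. Away from the incision the synopsis puts deficits in the same rule as allodynia and hyperalgesia. The difference is confined to numbness near the incision.
- A reader might infer that examiners will tick Absent on the brush item to mean no allodynia. The form also offers Normal, and Absent repeats the scale of the other items. The label is ambiguous, but nothing in the documents shows misuse.

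**Conclusion.** The concern holds for the summary. As written, SAP 8.6 gives no by-arm exam table in which hypersensitivity can be seen apart from expected numbness, and no shift from screening although the screening exam is collected. The test-location passages conflict. The adverse-event passages are inconsistent in wording and need harmonizing, but are not shown to contradict each other.

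The size is modest: a reporting weakness in a descriptive safety endpoint, with no effect on sample size, power or error rates. The percentages above rest on assumed counts and on 36 evaluable subjects per arm. They show what the table could hide and predict nothing. The verdict also assumes that the table shells follow the text of 8.6, since the shells are not in the documents.

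One limit should be stated plainly. A reader might expect the repaired tables to separate drug desensitization from surgical numbness. They cannot, because both are recorded as reduced or absent. Only the comparison with placebo addresses that.

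**What to change.** In SAP 8.6 and Tables 14.3.6.1 and 14.3.6.2:
- Tabulate each Appendix G item by its recorded categories, by treatment, foot and visit, with screening included.
- For brush, show gain (pain, hyperesthesia) and loss (reduced, absent) on separate rows.
- Add a shift from screening to each later visit. For brush, gain/normal/loss is enough, since a five-by-five table would be sparse at this sample size.

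The cost is a change to table shells and programming. All categories and the screening exam are already collected, and SAP section 1 places sign-off before database lock.

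Optionally, relabel the brush item 'Sensation to brush' so that Absent has one meaning. For forms already completed, Absent entries can be clarified by query.

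Separately, the sponsor should reconcile the test location across the synopsis (Monitored Parameters and Safety Parameter Assessment Times), Protocol 12.5.8 and SAP 8.6. It should also define *proximal*, *beyond* and *remote* consistently in the synopsis and 12.5.8. This review does not say which location or reporting rule is right. This part may need a protocol amendment, with IRB approval under Protocol 16.6 unless it counts as logistical or administrative.
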